6.2. Statistical analysis

Prior to analysis, descriptive statistics will be calculated to screen all variables for accuracy and to examine distributions.

All analyses will follow the intention-to-treat (“ITT”) principle, such that patients will be analyzed based on their assignment to the BH-VPN program or usual care. Balance in baseline characteristics between the groups will be assessed using Student’s t-test for normally distributed data, the Wilcoxon rank sum test for ordinal data or interval data that are not normally distributed, and the chi-square test for categorical data. Normality will be assessed using the Shapiro Wilk test and Q-Q plots.

The primary outcome, hospital admission (yes/no), is a binary dependent variable and will be compared between the BH-VPN and usual care groups using a generalized linear mixed-effects model with a logit link function. To adjust for correlation among patients seen on the same day and in the same ED, the model will include a random effect term for day nested within ED. The primary predictor in the model is an indicator for assignment to the BH-VPN program versus usual care. Additional baseline covariates will be included in the model if they are either strongly correlated with the dependent variable or show baseline imbalance between the two groups.

A similar approach will be used for the secondary outcomes to assess the patient-centric 45-day utilization rate, encounters with a self-harm diagnosis rate, and ED readmission rate. The models assessing these measures will be generalized linear mixed-effects models with a logit link, where utilization, diagnosis, or readmission, (yes/no) is the binary dependent variable. Independent variables in the models will be as described above for the primary analysis.

In addition, per-protocol analyses of the primary and secondary outcomes will be performed to evaluate the effect of BH-VPN program participation, in contrast to the ITT analysis evaluating the effectiveness of randomization to the program. The per-protocol analyses will include only subjects who received and adhered to the treatment (BH-VPN program or usual care).

Other binary outcome variables (e.g., frequency of patients active in the BH-VPN program) will be analyzed using descriptive statistics, unadjusted odds ratios, and 95% confidence intervals.

All tests will be two sided and the data will be analyzed using SAS Enterprise Guide 7.1 (SAS Institute Inc., Cary, NC, USA).

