
Inclusion/ Exclusion Criteria
	
Inclusion:
 
 • Present to an ED at participating sites • Complete a telepsychiatric consult as captured in the electronic medical record • Complete a telepsychiatric consult during the navigator’s hours of operation • ≥ 18 years of age at time of ED encounter 
Exclusion:
 
 • No exclusions

Study Procedures
	
Patients are identified by a clinician in the ED as needing psychiatric evaluation and a referral is made to a tele-psych provider for a virtual consult. Patients who complete a telepsychiatric consult in the ED can be enrolled to either the control or intervention arm based on a randomization scheme that randomly allocates days that navigators are available. Psychiatrists are reminded through daily communication as to whether the BH-VPN program is available and the ED locations. The psychiatrist will make a recommendation to admit or discharge the patient. For patients that have a discharge recommendation on days that BH-VPN is available, patients will be offered the BH-VPN program. Enrolled patients are followed for up to 45 days. Each patient will receive the following core components:
 
 1. Introduction to the patient follow-up process prior to discharge 2. Follow-up evaluation within 72 hours by phone and weekly contact 3. Confirm that an in-person follow-up visit with an appropriate provider or clinician is scheduled. Where applicable, confirm in-network follow-up appointments are completed. 4. Ongoing assessment: substance use disorder, medication barriers, and appointment barriers 5. Assist with community resources, crisis planning, and supportive listening 6. Placement into an appropriate case management program, if needed. 
On days where the navigator is available, all patients who meet eligibility criteria will be considered exposed to the intervention; whereas, on days the navigator is not available all patients will be considered exposed to usual care.

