4. SUBJECT AND SITE SELECTION

4.1. Accrual

As part of current care, patients are identified by a provider in the ED as needing psychiatric evaluation, and a referral is made to the telepsychiatric provider for a virtual consult. Patients are eligible to be included in analysis for the project if they meet the inclusion criteria and the telepsychiatric consultation occurs during potential BH-VPN program hours. We will accrue patient data for evaluation during a period starting in October 2019. Based on prior data, we estimate about 1,100 patients will complete a telepsychiatric consult in a 14-month period. Patients will not be accrued on days/times when the navigators would be not available (e.g. holidays).

Once a patient is in the intervention arm, the patient remains in the intervention arm until 45 days, or if there is a failure to contact (4 phone calls in 12 days), if the patient becomes enrolled with a case management program, declines services, or if the patient dies.

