5.2. Randomization and Allocation

Randomization will be based on days the navigators are available to treat patients who've completed their telepsychiatric consult. Patients may be in the ED for multiple days. Their enrollment status depends on the day and time of their initial telepsychiatric consultation. Navigation will only be available for those patients whose consult occurs during intervention day/times. As part of the research design and rollout of this project, randomization will occur at the day level with the days being identified as intervention or usual care days for the duration of the study. Patients will accrue in both arms of the study during the navigators' days and hours of operation. Patients will not be accrued on days where the navigators are not potentially available such as weekends, nights, and holidays.

Block randomization will be used to assign days the intervention is offered. In each 7-day period (Monday through Saturday) there will be three days the program is offered and three days where the program is not offered. The program is not available to patients in the ED on Sundays. The hours of availability are 7AM to 11PM Monday through Friday and 7AM to 7PM on Saturdays.

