5.3. Behavioral Health Virtual Patient Navigation (BH-VPN) Program

The BH-VPN outlines the flow of patients from initial contact to their follow-up calls (see Appendix 1). In the existing ED workflow, patients are identified by a clinician in the ED as needing psychiatric evaluation and a referral is made to a tele-psych provider for a virtual consult. Patients who complete a telepsychiatric consult in the ED can be enrolled to either the control or intervention arm based on a randomization scheme that randomly allocates days that navigators are available. Psychiatrists are reminded through daily communication as to whether the BH-VPN program is available and the ED locations. The psychiatrist will make a recommendation to admit or discharge the patient. The ED physician will make the final decision on whether to admit or discharge the patient from the ED. Patients that have a discharge recommendation on days the program is available, will be offered the BH-VPN program. Enrolled patients are followed for up to 45 days.

If a discharge recommendation is made, a patient will be approached again by the navigator virtually for enrollment into the BH-VPN program. The patient has the option not to be followed by the navigator. Before discharge, the navigator will complete an initial virtual behavioral health assessment. The initial health assessment contains information such as preferred communication method, primary care provider, psychiatry provider, PHQ-9 screening, collateral resources, recent ED and hospital utilization, substance use disorder, medication barriers, appointment barriers, community resources, and crisis planning.

The follow-up assessments, which will occur during navigation phone calls at least weekly, may include information such as a suicide ideation safety screening, an appointment reminder, appointment barrier evaluations, medication obtainment follow-up, substance use disorder follow-up, PHQ-9 screening, supportive listening, psychoeducation, community resource follow-up, and additional crisis planning. Phone calls are weekly as standard care but may be more often depending on the individual needs of the patient. Appointments are dependent on a patient's specific needs and may be with a therapist or psychiatrist as well as other providers in the community such as primary care or referral to a community provider.

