6.1. Sample size analysis and statistical analysis

Given the preliminary data from our previous study, we will power the proposed study to detect at least an 8% absolute difference between hospital admission in the VIBRANT intervention and usual care groups. The usual care group is assumed to have a 60% inpatient admission rate based on prior data. There is 85% power to detect this reduction with a total sample size of 1,030 ($\alpha=0.05$) using a Chi-square test for independence. To account for the possible correlation among patients seen in the ED on the same day, we inflated the sample size by 10% assuming the average number of patients per ED per day is 2 with a 0.1 intra-class correlation coefficient (design effect = $1 + (2-1)*ICC$).¹⁴ Thus, the target sample size is $n=1,133$. The power was calculated using PASS 15 Power Analysis and Sample Size Software (2017). NCSS, LLC. Kaysville, Utah, USA, ncss.com/software/pass.

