9. SAFETY RISKS AND REPORTING

The data collection and intervention for this project presents no more than minimal risk to patients. The implementation of the BH-VPN program and its components complement ongoing patient care through virtual patient navigation within Atrium Health. The BH-VPN program is currently offered at 10 urban EDs within Atrium Health. This study is evaluating the BH-VPN program among additional rural EDs that will offer the program to their patients. The addition of an evaluation design that aligns with existing patient care where there are limited resources thus confers minimal additional risk to patients.

Other potential risks of participation in this project include, the risk of health information disclosure. There is always the risk of disclosure of a patient's private health information (PHI) or medical information. However, the processes identified in this protocol to enable the execution of this project, do not increase inherent risk of disclosure. Atrium Health utilizes several hard and soft safety controls in the protection of patient information and medical records. Security controls include, but are not limited to, multiple system firewalls, access restrictions to patient records and information, locked offices and buildings housing research and patient data, and multiple layers of username and password protected computer and system access. The project team will ensure that appropriate handling of patient PHI follows standard Atrium Health procedure. In the event of PHI disclosure, the appropriate internal departments will be informed and processed per legislation and privacy regulations.

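### Days appear to be randomised on one schedule for all EDs, but the models and design effect cluster only on day within ED; the effect on the primary test is small and of uncertain direction

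*Combined protocol and SAP*

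**What the plan says.** Section 5.2 (Randomization and Allocation) sets the unit: "randomization will occur at the day level with the days being identified as intervention or usual care days for the duration of the study". In each Monday-to-Saturday week "there will be three days the program is offered and three days where the program is not offered". One pattern is described for the program as a whole; no schedule or stratification by ED is mentioned. The synopsis (Study Procedures) is consistent with this: "On days where the navigator is available, all patients who meet eligibility criteria will be considered exposed to the intervention".

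Several sites take part. Section 9 says: "This study is evaluating the BH-VPN program among additional rural EDs". Their number is not given.

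In Section 6.2 the primary model is a logistic mixed model in which "the model will include a random effect term for day nested within ED". The stated aim is to handle correlation among patients who share both day and ED. The secondary outcomes use a similar model. Section 6.1 inflates the sample size by 10%, "assuming the average number of patients per ED per day is 2 with a 0.1 intra-class correlation coefficient". Section 4.1 gives the volume: "we estimate about 1,100 patients will complete a telepsychiatric consult in a 14-month period".

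One sentence leaves room for a different reading of the schedule. Section 5.3 says: "Psychiatrists are reminded through daily communication as to whether the BH-VPN program is available and the ED locations".

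**The concern.** If one schedule applies everywhere, all patients seen on a given day share one assignment, whichever ED they attend. Treatment then varies only between days. A random effect for day within ED treats two patients at different EDs on the same day as independent. Anything that moves admissions at several EDs together on one day adds to the variance of the treatment contrast without entering its standard error. One possible source is the remote psychiatrist on duty, whose recommendation feeds the admission decision; the documents give no rota, so this is conjecture.

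At stake are the nominal 5% level of the primary test and the 1.10 design effect. The secondary models share the structure, but no size can be given for them because the plan states no intra-class correlation for those outcomes.

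Correlation that lasts the whole week behaves differently. Each week has three days in each arm, so a week-long shift largely cancels from the contrast.

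**Working it through.** **The plan's own figure.** Section 6.1: design effect = 1 + (2 − 1) × 0.1 = 1.10, and 1,030 × 1.10 = 1,133. The inflation step reproduces.

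**Patients per randomised day.** 14 months is 60.9 weeks; × 6 days = 365 randomised days, before holidays are removed. 1,100/365 = 3.0 and 1,133/365 = 3.1 per day over all EDs, if every consult falls in navigator hours.

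**Assumptions not in the documents.** ρ is the correlation between patients at different EDs on the same day; s is the share of ρ that lasts the whole week; K is the number of EDs (2 to 5). The 0.1 within an ED-day is the plan's.

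**Formulas.** Let a be the average number of other patients in the same ED-day, b the same-day patients at other EDs, and M the patients per day.

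- Design effect seen by the planned model: 1 + 0.1a.
- True design effect: 1 + 0.1a + bρ − Msρ. The last term is 5M patients on the other five days of the week, × sρ, × −1/5, the arm correlation of two days in a 3:3 block.
- Type I error = 2 × [1 − Φ(1.96 × √(model/true))].

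**Layouts.** The plan's averages taken as fixed sizes give a = 1, b = 1, M = 3. With Poisson counts, M = 3.1, a = 3.1/K and b = 3.1 − a.

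Worked case, K = 2, ρ = 0.05, s = 0: model 1 + 0.155 = 1.155; true 1.155 + 1.55 × 0.05 = 1.2325; type I error 5.8%. With s = 0.5 the added and cancelled terms are both 0.0775, so the error is 5.0%. With s = 1 the true value is 1.0775 and the error 4.2%.

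| Type I error | Plan's averages | K = 2 | K = 3 | K = 5 |
|---|---|---|---|---|
| ρ = 0.02, s = 0 | 5.2% | 5.3% | 5.4% | 5.5% |
| ρ = 0.05, s = 0 | 5.5% | 5.8% | 6.1% | 6.4% |
| ρ = 0.05, s = 0.5 | 4.7% | 5.0% | 5.3% | 5.5% |
| ρ = 0.05, s = 1 | 4.0% | 4.2% | 4.5% | 4.7% |
| ρ = 0.10, s = 0 | 6.1% | 6.6% | 7.2% | 7.8% |

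Inflation vanishes at s = b/M: 0.33, 0.50, 0.67 and 0.80 across the four layouts. K = 2 fits the plan's two patients per ED-day best: the mean per non-empty ED-day is 1.97 at K = 2, 1.60 at K = 3 and 1.34 at K = 5.

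**Simulation** (61 weeks, 3:3 blocks, one schedule for all EDs, null rate 60%, ρ = 0.05; 6,000 to 9,000 runs per cell, Monte Carlo SE 0.2 to 0.3 points). Each cell shows K = 2 / K = 5.

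| Analysis | s = 0 | s = 0.5 | s = 1 |
|---|---|---|---|
| Planned model | 5.7 / 6.4% | 5.2 / 5.3% | 4.3 / 4.5% |
| Random intercept for day instead | 5.2 / 5.2% | 4.7 / 4.3% | 3.7 / 3.6% |
| Day-clustered standard errors | 5.0 / 5.1% | 4.5 / 4.3% | 3.8 / 3.6% |

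**Power** at 1,133 patients, 60% vs 52%, pooled two-proportion formula, K = 2, s = 0: 71.4% at ρ = 0 (design effect 1.155), 70.3% at 0.02 (1.186) and 68.6% at 0.05 (1.2325).

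**The case against.** The strongest reply is that inflation needs three unstated things together: a common schedule, material correlation between EDs, and correlation that is mostly day-specific.

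- *Schedule.* The sentence in Section 5.3 on daily reminders can be read as availability that differs by ED. With separate schedules, day within ED would be about the right cluster and the point would largely fall away. But Section 9 says 10 urban EDs already offer the program, so psychiatrists may simply need to know where it runs. The doubt stands, and Section 5.2 should settle it.
- *Size.* Section 5.3 leaves the final decision to the local ED physician, which suggests a small correlation. With two EDs the worst case at ρ = 0.05 is under one point above nominal. This stands.
- *Volume.* Navigator hours are 5 × 16 + 12 = 92 of 168 per week. If the 1,100 counts all hours and consults arrive evenly, 3.1 × 92/168 = 1.7 patients per day remain, and the K = 2 figure at ρ = 0.05, s = 0 falls from 5.8% to about 5.5%. Section 4.1 can also be read as counting in-hours consults only.
- *Remedy.* Fitting both day and ED-by-day intercepts put one variance component at zero in 54% to 59% of simulated runs with no cross-ED correlation, and in 29% at day-specific correlation 0.05. A further week intercept showed no gain at s = 0.5 (5.5%, SE 0.4 to 0.5 points, against 5.2% as planned, K = 2). That argues for a single day-clustered analysis, not for leaving the model unchanged.

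**Conclusion.** The mismatch between the apparent unit of randomisation and the unit of clustering is real, and nothing else in the plan repairs it: there is no calendar-day effect, day-clustered variance or randomisation test. Its effect is small, and its direction depends on a correlation the plan does not state. For ρ of 0.02 to 0.05, type I error runs from about 5.2% to 6.4% if all the correlation is day-specific. It is about 5.5% or less if half or more lasts the week, and as low as 4.0% if all of it does. These figures rest on the inferred common schedule, two to five EDs and about three patients per day.

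A reader might infer more than the documents support:

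- *That the primary test is plainly anti-conservative.* The weekly blocking can make it conservative.
- *That the error reaches 7% to 8%.* That needs patients in different EDs to be as correlated as those in the same ED. Alternatively, it needs two patients a day in each of three EDs (7.1% at ρ = 0.05); six a day over 365 days is 2,190, about twice the accrual estimate.
- *That this explains the gap to the stated 85% power.* It does not. At 1,133 and the plan's own design effect of 1.10, the formula already gives 73.5%. That shortfall is a separate problem.

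**What to change.** 1. **Section 5.2:** state whether one schedule of intervention days covers all EDs. This is needed whatever the answer.
2. **Section 6.2, if the schedule is common:** make calendar day the clustering unit for the primary and secondary models, with day-clustered standard errors or a random intercept for day. Prespecify which. Additional ED-by-day and week terms need not be required.
3. **Section 6.1:** base the design effect on patients per randomised day (about three if all 1,100 consults fall in navigator hours, fewer otherwise). State a range for the day-level correlation and restate power over it.

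The cost is wording and one changed term, on data already held. With no cross-ED correlation, intervals were 1.0% to 1.3% wider in simulation; that figure comes from a model with both day and ED-by-day intercepts. Power with a day intercept alone was 70.3% against 71.6% for the planned model (K = 2) and 75.5% against 75.2% (K = 5), Monte Carlo SE 1.0 point. At ρ = 0.05 with all correlation lasting the week, day clustering is mildly conservative, 3.6% to 3.8% against 4.3% to 4.5% as planned.

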Study Objectives	
Primary objective:
 
 • Compare the effectiveness of having the Behavioral Health – Virtual Patient Navigation (BH-VPN) program available compared to usual care, on admission rates among patients in the ED with a telepsychiatric consult 
Secondary objectives:
 
 • Compare demographics and Charlson comorbidity score between the two arms of the study • Compare the patient-centric 45-day utilization rate after the ED visit (ED, IP, OBS, encounter) between the 2 arms of the study • Compare the frequency of patients with an encounter with a self-harm diagnosis within 45 days of the ED visit between the 2 arms of the study • Compare the frequency of patients who return to the ED and have a telepsychiatric consult within 45 days of their initial ED visit between the 2 arms of the study 
Reporting for the Duke Foundation:
 
 • Count/frequency of patients in the intervention and usual care arms presenting to an ED that have a telepsychiatric consult during the intervention • Count/frequency of patients with an admission after telepsychiatric consult in the intervention arm • Count/frequency of patients active in the BH-VPN • Count/frequency of patients active in the BH-VPN program that had an encounter with a self-harm code within 45 days of their ED visit • Count/frequency of patients active in the BH-VPN program that have an acute care visit (ED, IP, OBS) within 45 days of their ED visit • Count/frequency of patients active in the BH-VPN program that return to an Atrium Health emergency department with a telepsychiatric consult within 45 days of their ED visit • Count/frequency of patients active in the BH-VPN program that improve their PHQ-9 score, among patients with an initial score >10

	
 • Count/frequency of active in the BH-VPN program that report suicide ideation on their initial PHQ-9 (Q2>0), that no longer report suicide ideation on their last PHQ-9 (Q2=0) • Count/frequency of patients active in the BH-VPN program with successful case closure (complete the program or have a successful referral in care)

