Statistical Analysis	Analyses will include all patients identified as having completed telepsychiatric consult and meeting the inclusion criteria. Baseline comparisons of the intervention and usual care groups will be made using univariate analyses. The primary outcome, hospital admission, and secondary outcomes will be compared between the two groups of patients using generalized linear mixed-effects model with a logit link function. Results will be presented with odds ratios and 95% confidence intervals.
-----------------------------	--

LIST OF ABBREVIATIONS

BH-VPN	Behavioral Health - Virtual Patient Navigation
CORE	Center for Outcomes Research and Evaluation
C-SSRS	Columbia – Suicide Severity Rating Scale
DHHS	Department of Health and Human Services
EHR	Electronic Health Record
ED	Emergency Department
EDW	Enterprise Data Warehouse
FY	Fiscal Year
NC	North Carolina
OCTR	Office of Clinical and Translational Research
PHI	Private Health Information
SOP	Standard Operating Procedures

TABLE OF CONTENTS

1.1.	Hypothesis.....	8
1.2.	Primary Objective.....	8
1.3.	Secondary Objectives.....	8
1.4.	Reporting for the Duke Foundation.....	8
2.	BACKGROUND.....	9
3.	RATIONALE.....	10
4.	SUBJECT AND SITE SELECTION.....	10
4.1.	Accrual.....	10
4.2.	Eligibility Criteria.....	11
4.2.1.	Inclusion Criteria.....	11
4.2.2.	Exclusion Criteria.....	11
4.3.	Evaluable Population.....	11
5.	OVERALL DESIGN.....	11
5.1.	Outcome Variables.....	11
5.1.1.	Primary Outcome Variable.....	11
5.1.2.	Rates and Variable Descriptions.....	11
5.1.3.	Reporting for the Duke Foundation.....	12
5.2.	Randomization and Allocation.....	12
5.3.	Behavioral Health Virtual Patient Navigation (BH-VPN) Program.....	13
5.4.	Follow-up.....	14
5.5.	Patient Graduation from the BH-VPN Program.....	14
5.6.	Continuation of the Intervention.....	14
6.	DATA COLLECTION AND REPORTING.....	14
6.1.	Sample size analysis and statistical analysis.....	15
6.2.	Statistical analysis.....	15
6.3.	Data Collection Dates.....	16
7.	INTERVENTION PLAN.....	16
7.1.	Navigator Assessments.....	16
7.2.	Follow-up Assessments.....	16
8.	STUDY GOVERNANCE.....	17
8.1.	Protocol and Pathway Training.....	17

9. SAFETY RISKS AND REPORTING	17
9.1. Data Quality Assurance	18
9.2. Data Monitoring by the Sponsor	18
10. RESEARCH COMPLETION	18
11. ETHICAL AND LEGAL ISSUES	19
11.1. Ethical and Legal Conduct of the Study	19
11.2. Confidentiality	19
11.3. Disclosure of Data	19
12. RETENTION OF RECORDS	20
13. PUBLICATION POLICY	20
REFERENCES	21

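### Section 6.2 picks the covariates of the primary and secondary models from the trial's own data; a list fixed in advance removes an outcome-dependent choice, with a small and assumption-dependent effect on power

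*Combined protocol and SAP*

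**What the plan says.** The primary outcome, admission yes or no, is to be analysed with a logit mixed model. In Section 6.2, "the model will include a random effect term for day nested within ED", and the main predictor is assignment to the navigation programme. Further baseline covariates are then "included in the model if they are either strongly correlated with the dependent variable or show baseline imbalance between the two groups".

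The same section states that "Balance in baseline characteristics between the groups will be assessed using" t, Wilcoxon or chi-square tests according to the type of variable. It gives no significance level for calling a variable imbalanced, and neither a measure nor a cut-off for a strong correlation.

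For the secondary outcomes, "Independent variables in the models will be as described above for the primary analysis". The synopsis (Statistical Analysis) says only that outcomes are "compared between the two groups of patients using generalized linear mixed-effects model with a logit link function" and names no covariates.

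The plan does name baseline variables elsewhere. A secondary objective in the synopsis is to "Compare demographics and Charlson comorbidity score between the two arms of the study", and Section 5.1.2 lists age, race, gender and the Charlson index. Section 6 draws demographics, comorbid conditions and utilization from the medical record and billing systems, and allows retrieval after a patient has finished the study arm.

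**The concern.** Both entry conditions are judged on trial data, and one of them uses the primary outcome itself. Two statisticians following the text could fit different primary models.

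Three consequences follow even if everyone acts in good faith:

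- **Meaning of the estimate.** A logit odds ratio is conditional on the covariates in the model as well as on the random effect. The covariate part is left open until outcomes are known.
- **Lost precision.** Several covariates can each be too weak to count as strongly correlated and still matter jointly.
- **Chance entry.** Days are randomised (Section 5.2), so an imbalance between arms is a chance event. The imbalance condition admits variables whether or not they predict admission.

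At stake are a little power and the pre-specification of the primary analysis.

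**Working it through.** **1. The plan's own power figure.** Inputs from Section 6.1: "The usual care group is assumed to have a 60% inpatient admission rate based on prior data", an 8-point reduction (60% to 52%), 85% power, alpha 0.05, and N = 1,030 before a 10% inflation "assuming the average number of patients per ED per day is 2 with a 0.1 intra-class correlation coefficient". Tests are two-sided (Section 6.2).

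n per arm = [1.960·√(2·0.56·0.44) + 1.036·√(0.60·0.40 + 0.52·0.48)]² / 0.08² = (1.376 + 0.725)² / 0.0064 ≈ 690, or 1,380 in total.

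At 515 per arm: z = (0.08·√515 − 1.376)/0.700 = 0.63, which is 73.5% power. The stated 85% is not reproduced. The inflation is (1,030 × 1.1 = 1,133). The shortfall is a separate matter, but it explains why the power figures below start near 73%.

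**2. Chance imbalance.** For four independent candidates at an assumed p<0.05: 1 − 0.95⁴ = 18.5% of trials flag at least one. Simulated: 17.5–19.4%.

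**3. What a correlation cut-off discards.** With covariate effects of 0.1, 0.3 and 0.5 log-odds per SD, the correlation with admission is about 0.04, 0.12 and 0.19–0.21. None reaches 0.3. Yet four independent covariates at r = 0.12 jointly explain about 4 × 0.12² = 5.8% of outcome variance.

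**4. Power of a fixed list against the rule, same four candidates.** There were 2,500 simulated trials per scenario: 567 ED-days of 2 patients (N = 1,134), 60% v 52%, ICC 0.10, and a logistic model with a random intercept for ED-day. Assumptions: four independent standard-normal covariates; arm assigned by ED-day; no separate ED or shared-day effect; imbalance at p<0.05; a strong correlation read as |r| above 0.3, 0.2 or 0.1.

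| Log-odds per SD | No covariates | Rule, \|r\|>0.3 / 0.2 / 0.1 | Fixed four | Fixed minus rule (points) |
|---|---|---|---|---|
| 0.1 each | 72.3% | 72.3 / 72.3 / 72.2% | 72.6% | 0.3 / 0.3 / 0.4 |
| 0.3 each | 73.1% | 73.5 / 73.4 / 75.6% | 76.0% | 2.5 / 2.6 / 0.4 |
| 0.5, 0.3, 0.2, 0.1 | 72.4% | 72.8 / 73.9 / 75.4% | 75.4% | 2.6 / 1.5 / 0.0 |
| 0.5 each | 72.7% | 73.5 / 75.1 / 78.2% | 78.2% | 4.7 / 3.1 / 0.0 |

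No part of the documents supports the strength assumed in the last row. At |r|>0.3 the rule keeps on average 0.2 of the four covariates in every row, almost all through chance imbalance.

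A second simulation (8,000 trials, cluster-robust logistic model, N = 1,132) gave gains over the rule of about −0.1 points with no prognostic value, 0.3–0.4 at R² 1.3% and 0.4–1.6 at R² 4.8%. A third gave 0.1–0.3 (0.1 each), 0.4–1.6 (0.3 each) and 0.5–2.8 (mixed).

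**5. Shift in the estimate.** At 0.3 per SD the mean log odds ratio is −0.392 with the fixed list and −0.363 under the rule at |r|>0.3. That is exp(−0.392) = 0.68 against exp(−0.363) = 0.70, a difference of 0.029 against a standard error of about 0.15.

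**6. Type I error.** First simulation: rule 4.2–5.5%, fixed list 4.7–5.5%. Second: 4.7–5.1% and 4.8–5.0%.

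**7. When the fixed four omit a stronger variable.** Section 6.2 does not limit the candidates to four. One further baseline variable was added and offered to the rule only (3,000 trials, cluster-robust logistic model).

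| Listed four | Extra variable, r with admission | Fixed four | Rule | Fixed minus rule (points) |
|---|---|---|---|---|
| 0.1 each | about 0.32 | 73.3% | 76.6–77.5% | −3.3 to −4.2 |
| 0.1 each | about 0.21 | 74.2% | 74.4–75.3% | −0.2 to −1.1 |
| 0.3 each | about 0.30 | 76.2% | 77.9–80.1% | −1.7 to −3.9 |

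A repeat of this check put the loss at about 0.2–5 points for an extra variable with r of about 0.2–0.3.

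**The case against.** The strongest reply is that the rule is open-ended by design. It can pick up whatever baseline variable turns out to predict admission, including prior utilization, and a list confined to four variables cannot. Step 7 bears this out: a reader might infer from step 4 that fixing the four never costs power, but that holds only when the rule is offered the same four. This part of the objection stands, and it is why the list below is wider.

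Second, the 0–3 points depend on the cut-off read into the text (at 0.3 per SD the gain is 2.6 points at |r|>0.2 but 0.4 at |r|>0.1) and on the starting power. Against no adjustment, R² of 5% gives +2.2 points from a 73.5% base and +1.7 from 85%. The simulated covariates are independent normals, whereas gender is binary and race categorical. These limits also stand; the figures are indicative.

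Third, forcing in the Charlson score could do harm. The documents state no look-back, and data may be retrieved retrospectively from records and billing. Codes added during an index admission would then depend on the primary outcome. The current rule carries the same risk, but unconditional inclusion makes it certain to matter, so the fix must close it.

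A reader might also go the other way and infer that outcome-dependent selection invalidates the primary test. The documents do not support that. Applied mechanically, the rule holds its level (step 6). If an analyst were free to pick the best of the 16 subsets of four covariates, type I error would be about 5.7%, 7.3% and 9.1% at R² of 1%, 4% and 9% (linear model, no clustering). That is a ceiling under deliberate selection, which nothing in the plan proposes.

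**Conclusion.** The point holds as one of pre-specification. The covariates of the primary and secondary models are chosen from trial data, including the outcome, without cut-offs or a closed list, although the plan already names suitable variables. The main benefit of a fixed list is that it removes this choice.

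The power effect is secondary: about 0 to 3 points over the rule if the four named variables are the only candidates and are weakly to moderately prognostic, negligible if they are weak, and negative if a stronger baseline variable is left off. All of this rests on assumed covariate strengths, an assumed p<0.05 for imbalance and an assumed reading of a strong correlation.

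Nor should covariate adjustment be read as a remedy for the sample-size shortfall in step 1: from 73.5%, R² of 7% reaches only about 77%.

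**What to change.** Before outcome data are extracted, replace the selection sentence in Section 6.2 with wording such as:

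> The primary and secondary models will adjust for age, gender, race, Charlson comorbidity score and [any further pre-consult variable named here], regardless of observed balance or association with the outcome.

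In the same place:

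- Name any other baseline variable already extracted for both arms that the sponsor judges prognostic beforehand, for example prior utilization. Take it from the record and billing systems, not from the navigator's assessment, which is done only for patients approached for the programme.
- Compute the Charlson score and any utilization covariate only from diagnoses and encounters recorded before the index telepsychiatric consult.
- State the coding: age and Charlson score linear, race categories set in advance, missing gender or race as its own category.
- For the self-harm model, name one short unconditional list, for example age and gender. The documents give no self-harm rate; an assumed 1–5% of 1,133 is only 11–57 events.
- Report baseline characteristics descriptively, and do not use balance tests to choose covariates.
- Report the mixed model without covariates as a sensitivity analysis.

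The planned random effect is outside this point and can stay as written.

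The cost is a few sentences, no new data collection and a few degrees of freedom (race takes one per category beyond the first). The remaining downside is a possible small loss of power if a strong predictor is left off the list.
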